## LIST OF ABBREVIATIONS

AE	Adverse Event
AED	Antiepileptic Drug
BMI	Body Mass Index
BRV	Brivaracetam
CRF	Case Report Form
C-SSRS	Columbia-Suicide Severity Rating Scale
CT	Computerized Tomography
DEM	Data Evaluation Meeting
DRC	Daily Record Card
ECG	Electrocardiogram
EDV	Early Discontinuation Visit
EEG	Electroencephalogram
ES	Enrolled Set
FAS	Full Analysis Set
IMP	Investigational Medicinal Product
LTFU	Long-Term Follow-Up
MedDRA	Medical Dictionary for Regulatory Activities
MRI	Magnetic Resonance Imaging
PCST	Possibly Clinically Significant Treatment-emergent
PDILI	Potential Drug-Induced Liver Injury
PT	Preferred Term
SAE	Serious Adverse Event
SAP	Statistical Analysis Plan
SD	Standard Deviation
SOC	System Organ Class
SS	Safety Set
TEAE	Treatment-Emergent Adverse Event
VNS	Vagus Nerve Stimulation
WHODD	World Health Organization Drug Dictionary
28DPSF	28-Day Adjusted Partial Seizure Frequency

## 1 INTRODUCTION

This statistical analysis plan (SAP) defines the scope of statistical analyses and provides a detailed description of statistical methodology for the statistical analyses to support the final clinical study report (CSR). The SAP is based on the following study document: Protocol Amendment 4.1 and Case Report Form (CRF) version 8.0.

## 2 PROTOCOL SUMMARY

### 2.1 Study objectives

#### 2.1.1 Primary objectives

The primary objective is to evaluate the long-term safety and tolerability of BRV in focal epilepsy subjects with partial seizures.

#### 2.1.2 Secondary objective

The secondary objective is to evaluate the maintenance of efficacy of BRV over time.

### 2.2 Study variables

#### 2.2.1 Safety variables

##### 2.2.1.1 Primary safety variables

The primary safety variable is treatment-emergent adverse events (TEAEs).

##### 2.2.1.2 Other safety variables

The other safety variables are as follows:

- Laboratory tests (blood chemistry, hematology, and urinalysis)
- Vital signs
- Body weight
- 12-lead electrocardiogram (ECG)
- Physical examination
- Neurological examination

#### 2.2.2 Efficacy variables

The efficacy variables for rollover subjects in China and Japan include:

- Percent reduction in partial seizure frequency per 28 days from Baseline of EP0083 or N01358 to the Evaluation Period
- Responder rate in partial seizure frequency per 28 days over the Evaluation Period. A responder is defined as a subject with a  $\geq 50\%$  reduction in partial seizure frequency from the Baseline Period of EP0083 or N01358

Efficacy variables for direct enrollers in Japan include:

- Percent reduction in partial seizure frequency per 28 days from 8 weeks prior to BRV administration to the Evaluation Period

- Responder rate in partial seizure frequency per 28 days over the Evaluation Period. A responder is defined as a subject with a  $\geq 50\%$  reduction in partial seizure frequency from 8 weeks prior to BRV administration

Efficacy variables for all subjects (rollovers in China and Japan and direct enrollers in Japan):

- Percentage of subjects continuously seizure-free for partial seizures and all seizure types (partial, generalized and unclassified epileptic seizure) for at least 6 months and at least 12 months during the Evaluation Period
- Seizure freedom (partial, all epileptic seizure) during the Evaluation Period

## 2.3 Study design and conduct

EP0085 is a Phase 3, open-label, long-term follow-up (LTFU), multicenter, noncomparative, and dose flexible study being conducted in Japan and China. The population are subjects ( $\geq 16$  years of age) with partial seizures with or without secondary generalization. Subjects of a minor age are included only where legally permitted and ethically accepted. In Japan, subjects meeting the inclusion and exclusion criteria as specified in the study protocol can be directly enrolled.

Rollover subjects must complete the Treatment and Transition Period of EP0083 prior to enrolment into EP0085. In addition, Japanese subjects participating in N01379, the long-term open-label extension to the Phase 3, placebo-controlled study N01358, can enter this study. Upon completion or early discontinuation from EP0085, there will be a Down-Titration Period, followed by a 2-week Study Drug-Free Period during which the subject will not receive study drug.

Directly enrolled subjects in Japan will have their eligibility confirmed at the Screening Visit (SV). SV occurs -2 to -21 days before BRV administration. Directly enrolled subjects in Japan and rollover subjects from EP0083 will be started on oral BRV at a dose of 100mg/day (2 equally divided doses administered twice daily) at study entry and should be maintained at this dose for at least 2 weeks, unless the subject is unable to tolerate treatment.

Subjects from N01379 can enter EP0085 at a dose up to 200mg/day. After Visit 1, the next visit for subjects entering from N01379 will be Visit 4 (Visit 2 and Visit 3 will not be conducted). Subsequent visits will be conducted according to the visit schedule according to EP0085 study protocol. (see [Table 1](#)). The BRV dose can be adjusted based on the individual subject's seizure control and tolerability between 50mg/day and 200mg/day during the study and must always be administered as a symmetrical morning and evening dose except the last week of down-titration. Of note, decreasing the dose should not exceed 50mg/day. Study drug in the last week of down-titration is given only in the morning.

The study duration per subject is defined as follows:

- Screening Visit (Visit 0, up to 3 weeks before the Entry Visit (EV) for direct enrollers in Japan only)
- Evaluation Period (Visit 1 to End of Study Visit or Early Discontinuation Visit [EDV]): Subjects who enroll in EP0083 and N01379 will enter the Evaluation Period
- Down-Titration Period (up to 4 weeks):

---

- If the subject is discontinuing study drug, the Investigator will first plan an EDV followed by the progressive down-titration of study drug.
- During the Down-Titration Period, the BRV dose may be decreased in steps of a maximum of 50mg/day on a weekly basis. A last down-titration step at 25mg/day for 1 week should be included prior to the 2-week Study Drug-Free Period.
- 2-week Study Drug-Free Period: After completion of the Down-Titration Period, or for those subjects who for extenuating circumstances do not complete a Down-Titration Period, the subject will be required to enter a 2-week Study Drug-Free Period, followed by a Final Visit (FV).

Subjects who will be converted to the commercial BRV product will complete an End of Study Visit without entering the Down-Titration Period or the 2-week Study Drug-Free Period and will not complete an FV.

Visits should occur on the specified Visit/Week. A  $\pm 7$  day window for each specified Visit/Week is allowed, provided the subject has adequate investigational medicinal product (IMP) to sustain the visit window. The end of the study is defined as the date of the last visit of the last subject in the study.

EP0085 will continue until the market approval of BRV, or until the sponsor decides to close the study, whichever comes first. In the event that market approval is not requested or obtained in the participant country, the subject will be able to continue in EP0085 for two years after entering EP0085.

In Japan, EP0085 will continue as a postmarketing clinical study (Phase 4) after the date of approval of BRV for the partial seizure indication.

At selected sites in Japan, Japanese subjects may participate in an additional study (EP0118) with the intravenous formulation of BRV without withdrawing from EP0085. Ten evaluable subjects are planned for EP0118, and the total duration in the study for each subject is 7 days. The study period of EP0118 will be included in that of EP0085. Subjects will continue to receive their current dose of BRV at the time of entry and it will remain stable for the duration of EP0118. Subjects who complete or withdraw from EP0118 will resume their participation in EP0085 with oral BRV treatment. In the event that a subject withdraws from EP0118 and is required to down-titrate BRV treatment, the subject will return to EP0085 and down-titrate using BRV tablets. TEAEs and concomitant treatment(s)/medication(s) that occur or are administered during EP0118 will be recorded in EP0118. Ongoing TEAEs and concomitant medication(s)/medical procedure(s) originating from EP0118 will be recorded and followed in EP0085 until resolution or until the status of the TEAE and/or concomitant medications are stable. All other data reported for EP0118 will be captured in the EP0118 database. Per the EP0118 protocol, the study (EP0118) will require hospitalization. Hospitalization for study participation does not need to be reported as an SAE.

**Table 1: Full visit schedule**

First year follow-up		
Month (Week)	Visit	Type of visit
-2 to -21 days	V0	SV a
M0 (W0)	V1	EV
M1 (W4)	V2 c	MEV b
M2 (W8)	V3 c	FEV
M3 (W12)	V4	MEV b
M4 (W16)	-	-
M5 (W20)	-	-
M6 (W24)	V5	FEV
M7 (W28)	-	-
M8 (W32)	-	-
M9 (W36)	V6	MEV b
M10 (W40)	-	-
M11 (W44)	-	-
M12 (W48)	V7	YEV
Second year follow-up c		
Month	Visit	Type of visit
M15 (W60)	V8	MEV b
M18 (W72)	V9	FEV
M21 (W84)	V10	MEV b
M24 (W96)	V11	YEV

EV=Entry Visit; FEV=Full Evaluation Visit; M=month; MEV=Minimal Evaluation Visit; SV=Screening Visit; V=Visit; W=Week; YEV=Yearly Evaluation Visit

Note: A dash (-) denotes that no visit is scheduled in that month.

a For subjects directly enrolled into EP0085 in Japan only.

b Laboratory safety assessments will not be performed at MEV. Only liver function tests will be performed at MEV in the first year (V4 and V6).

c Subsequent years will follow the same visit schedule.

## 2.4 Determination of sample size

For this open-label LTFU study, no sample size calculation was performed. The sample size will depend upon recruitment into and completion of the previous studies. Overall, approximately 217 subjects are planned for enrollment. In Japan, it is estimated that approximately 127 subjects will enter the study. This estimate assumes that at least 90% of randomized Japanese subjects will complete EP0083 (approximately 90 subjects) or enroll from N01379 sites in Japan (7 subjects) and that 30 Japanese subjects will be directly enrolled in this study. Likewise, this estimate assumes that at least 90% of randomized Chinese subjects will complete EP0083 (approximately 90 subjects).

## 3 DATA ANALYSIS CONSIDERATIONS

### 3.1 General presentation of summaries and analyses

For the analysis purposes, “core study” in this plan refers to the study where the subjects were firstly enrolled. For rollover subjects, the core study is N01358 (for rollover subjects from N01379) or EP0083 (for rollover subjects from EP0083). For direct enrollers EP0085 is the core study.

Statistical analysis and generation of tables, figures, subject data listings, and statistical output will be performed using SAS® Version 9.3 or higher.

Descriptive statistics will be displayed to provide an overview of the study results. For categorical parameters, the number and percentage of subjects in each category will be presented. The denominator for percentages will be based on the number of subjects appropriate for the purpose of analysis. Unless otherwise noted, all percentages will be displayed to 1 decimal place. No percentage will be displayed for zero counts, and no decimal will be presented when the percentage is 100%.

For continuous parameters, descriptive statistics will include number of subjects with available measurements (n), mean, standard deviation (SD), median, minimum, and maximum. Decimal places for descriptive statistics will always apply the following rules:

- “n” will be an integer.
- Mean, SD and median will use 1 additional decimal place compared to the original data.
- Minimum and maximum will have the same number of decimal places as the original value.

All summaries will be descriptive; no statistical hypothesis testing is planned.

Subject data listings will be provided and will present source data and key derived variables for statistical analyses.

### 3.2 Analysis time points

#### 3.2.1 First and last dose of BRV

Unless otherwise noted, all references to the first dose of BRV in this SAP refer to the first dose of BRV during EP0085 (ie, not the first dose of BRV from the previous study in which subjects participated in prior to EP0085). Unless otherwise noted, all references to the last

known dose of BRV in this SAP refer to the last dose of BRV taken across any study periods (ie, the last dose of BRV across both the Evaluation and Down-Titration Periods).

### 3.2.2 Relative day

Relative day will be calculated as follows:

- For days prior to the first dose of BRV, the relative day is the current date minus the date of first dose of BRV. The relative day prior to first dose will be Day -1.
- For days on or after the first dose of BRV and on or prior to the last dose of BRV, the relative day is the current date minus the date of first dose of BRV plus 1. The relative day of first dose will be Day 1.
- For days after the last dose of BRV, the relative day is the current date minus the date of last dose of BRV. The relative day will include a “+” to denote post treatment days (eg, the day after the last dose will be Day +1).

Relative day will not be calculated for partial or missing dates.

### 3.2.3 Screening Visit

The SV only applies to direct enrollers in Japan and will be performed between Day -21 and Day -2 prior to Visit 1 (EV). The following assessments will be performed at SV:

Study	Visit	Assessments
EP0085 direct enrollers in Japan	Visit 0	Demography, medical history, epilepsy history, AED history, vital signs, body weight, physical examination, neurological examination, 12-lead ECG, electroencephalogram (EEG), neuro-imaging procedure (per Investigator discretion), laboratory safety assessments, seizure counts, ongoing AE reporting (see more information in Section 9.2), C-SSRS, medical procedures, ongoing concomitant medications (including AEDs and non-AEDs).

### 3.2.4 Entry Visit

The EV corresponds to the assessments performed at the time of entry into EP0085. For direct enrollers in Japan, the EV will be performed at Visit 1 and the relevant assessments will be performed according to the study protocol. For rollover subjects from EP0083 and N01379, the following assessments will be completed during the last visit of the previous study and do not need to be repeated at Visit 1:

Study	Visit	Assessments
EP0083	Visit 8	vital signs, body weight, physical examination, neurological examination, 12-lead ECG, laboratory safety assessments, seizure counts, ongoing AE reporting (see more information in
N01379	Last Evaluation Period Visit or Early Discontinuation Visit	vital signs, body weight, physical examination, neurological examination, 12-lead ECG, laboratory safety assessments, seizure counts, ongoing AE reporting (see more information in

		Section 9.2), C-SSRS, medical procedures, ongoing concomitant medications (including AEDs and non-AEDs).
--	--	--

### 3.2.5 Study periods

The following study periods are defined for the classification in summary that are based on the study design:

Baseline Period	For rollover subjects from EP0083, the Baseline Period corresponds to the Baseline Period of EP0083 and is defined as study days on or after EP0083 Visit 1 date and prior to EP0083 Visit 3 date.  For rollover subjects from N01379, the Baseline Period corresponds to the Baseline Period of N01379 and is defined as study days on or after N01358 Visit 1 date and prior to N01358 Visit 3 date.  For direct enrollers, except for seizure outcome the Baseline Period is defined as study days on or after EP0085 Visit 0 date and prior to EP0085 Visit 1 date. The Baseline Period for seizure outcome is defined as 8 weeks prior to the first BRV administration (see section 8.1.2).
Evaluation Period	The Evaluation Period starts on the date of Visit 1 and the following algorithm is used to determine the end date:  If the subjects enter the Down-Titration Period: 

- for completed subjects, which is indicated by the CRF “Study Termination” form (Complete subject), the Evaluation Period ends on the date of End of Study Visit date.

- for discontinued subjects, which is indicated by the CRF “Study Termination” form (Dropout), the Evaluation Period ends on the date of EDV date.

 If the subjects do not enter the Down-Titration Period:  For complete / discontinued subjects who do not enter the Down-Titration Period, the end of Evaluation Period will be the date of last dose of BRV.
Down-Titration Period (up to 4 weeks)	If the subject is discontinuing BRV, the Investigator will first plan an EDV followed by the progressive down-titration of study drug.

A subject is considered entering Down-Titration Period only if the subject has an EDV and has at least 1 dose of study drug after the date of EDV, the start date of Down-Titration Period is set as 1 day after the date of EDV, and the Down-Titration Period ends on date of last dose of BRV. A subject without an EDV but having a termination CRF or with an EDV but without any dosing of study drug after the EDV will not have the Down-Titration Period, and no artificial Down-Titration Period will be created for analysis.

Study Drug-Free Period (2 weeks)

After completion of the Down-Titration Period, or for those subjects who for extenuating circumstances do not complete a Down-Titration Period, the subject will enter a 2-week Study Drug-Free Period, followed by a Final Visit.

A subject is considered entering the Study Drug-Free Period if the subject has at least 1 contact (scheduled visit, unscheduled visit, or telephone contact) after the date of last dose of BRV. The 2-week Study Drug-Free Period starts 1 day after the date of last dose of BRV and ends on the date of Final Visit, irrespective of entering the Down-Titration Period.

A subject is considered as completed if this subject completes all scheduled visits as defined in the protocol or converts to commercial BRV without a Down-Titration Period (where commercial BRV is available).

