Visit	V1	V2 ^a , V4, V6, V8, V10…	V3 ^a , V5, V9…	V7, V11…	NA	NA
Month	M0	M1, M3, M9, M15, M21…	M2, M6, M18…	M12, M24…	NA	NA
Week	W0	W4, W12, W36, W60, W84…	W8, W24, W72…	W48, W96…	NA	NA

Note: For subjects who have completed EP0083 or N01379, assessments marked (*) should have already been completed during the last visit of the previous protocol and do not need to be repeated at Visit 1.

^a After Visit 1, for subjects entering from N01379 V2 and V3 will not be conducted. Subsequent visits will be conducted according to the visit schedule provided in Table 5–3.

^b Informed consent must be obtained during the previous study.

^c General medical and procedures history, AED history, and epilepsy history will be obtained from the Baseline of EP0083 or Baseline of N01358 (for subjects entering from N01379) and do not need to be recorded on the eCRF for this study.

^d Height will be recorded at V1 only.

^e At the FV, a 12-lead ECG is mandatory, except if the FV follows an EDV where ECG results were normal.

^f Seizure counts are collected on the subject's daily record card on a daily basis.

^g Laboratory safety assessment will not be performed at MEV. Only liver function tests will be performed at the MEV in Visit 4 (M3) and Visit 6 (M9). Laboratory safety assessment is mandatory at the FV, except if the FV follows an EDV where laboratory results were normal. The result of the calculated creatinine clearance will be provided by the central laboratory.

^h A urine pregnancy test will be done for female subjects with childbearing potential.

ⁱ End of study status will be completed at the FV for subjects having performed an EDV and down-titration of BRV (discontinued subjects) and for subjects leaving the study at the end of the program (completed subjects). Alternatively, end of study status will be completed at the End of Study Visit for subjects who will be converted without down-titration to commercial BRV if, when, and where available.

Table 5-2: Schedule of study assessments for subjects directly enrolled into EP0085 in Japan

Assessments	SV	EV	MEV	FEV	YEV	End of Study Visit or EDV	FV
Visit	V0	V1	V2, V4, V6, V8, V10...	V3, V5, V9...	V7, V11...	NA	NA
Month	-	M0	M1, M3, M9, M15, M21...	M2, M6, M18...	M12, M24...	NA	NA
Week	(-2 to -21 days)	W0	W4, W12, W36, W60, W84...	W8, W24, W72...	W48, W96...	NA	NA
Written informed consent	X						
Subject identification card dispensed	X						
Eligibility assessment	X	X					
Demography	X						

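### SAP 3.2.5 gives completers who taper an Evaluation Period end date, but lets nobody into Down-Titration without an EDV, so a completer's taper days can stay in the Evaluation Period

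*SAP*

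**What the plan says.** All the conflicting text is in the current SAP 3.2.5.

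- **Evaluation Period, subject enters Down-Titration.** For a completed subject, "the Evaluation Period ends on the date of End of Study Visit date". For a dropout it ends at the EDV.
- **Evaluation Period, subject does not enter Down-Titration.** For completed and discontinued subjects alike, "the end of Evaluation Period will be the date of last dose of BRV". SAP 3.2.1 defines that dose as "the last dose of BRV across both the Evaluation and Down-Titration Periods".
- **Entry to Down-Titration.** "A subject is considered entering Down-Titration Period only if the subject has an EDV and has at least 1 dose of study drug", with the dose falling after the EDV date.
- **Start of Down-Titration.** "the start date of Down-Titration Period is set as 1 day after the date of EDV".
- **No EDV.** "A subject without an EDV but having a termination CRF" has no Down-Titration Period, and the SAP says it will not construct one.
- **Completed.** A subject who "completes all scheduled visits as defined in the protocol or converts to commercial BRV without a Down-Titration Period". Completing all visits and converting are two separate routes.

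The protocol keeps the visit labels apart in the same way. Table 5-1 footnote i speaks of "subjects having performed an EDV and down-titration of BRV (discontinued subjects") and lists completed subjects, who leave at the end of the program, as a separate group. Protocol 5.1.1 ends the Evaluation Period at the End of Study Visit or the EDV. Protocol 5.1 and SAP 2.3 place a Down-Titration Period after completion as well as after early discontinuation; SAP 2.3 exempts converters to commercial product.

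**The concern.** The SAP has a rule for completers who taper, but its entry condition keeps a completer with only an End of Study Visit from reaching it. That subject falls to the last-dose rule, so the Evaluation Period absorbs the taper, contrary to protocol 5.1.1. The subject also drops out of the Down-Titration summaries that protocol 12.4 plans for all subjects.

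What would change:

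- By-period TEAE tables, because SAP 9.2.2 assigns events to periods by onset date.
- Disposition by study period (SAP 5.1).
- Whole-period seizure frequency, percent reduction and seizure freedom. SAP 8 takes all seizure records in the Evaluation Period, and a diary is in use during taper: it is dispensed at the End of Study Visit (protocol 8.7) and collected at the Final Visit (8.8).

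What would not change: overall TEAE incidence, the 3-month TEAE intervals, exposure, time to BRV discontinuation, and anything for commercial converters.

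**Working it through.** **1. Does the plan foresee such subjects?** Yes. Taper follows completion (protocol 5.1). Where approval is not requested or obtained, subjects may stay for two years (5.1.1). Footnote i sends completers leaving at the end of the program to a Final Visit, which converters do not have (8.8).

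**2. Length of taper.** Inputs: doses of 50 to 200 mg/day, weekly steps of at most 50 mg/day, and a final week at 25 mg/day (SAP 2.3). Using maximum steps:

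- 50 mg/day: 25 = 7 days
- 100 mg/day: 50, 25 = 14 days
- 150 mg/day: 100, 50, 25 = 21 days
- 200 mg/day: 150, 100, 50, 25 = 28 days

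The longest is 4 weeks, which reproduces the SAP's stated maximum.

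**3. The algorithm applied literally.** The first dose is on the day of Visit 1, so Week 96 is Day 96 × 7 + 1 = 673. Take a closing visit on Day 673 and, for those who taper, a last dose on Day 673 + 28 = 701.

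| Subject | Evaluation Period ends | Down-Titration |
|---|---|---|
| Dropout with EDV, tapers | Day 673 | Day 674–701 |
| Converter, last dose Day 673 | Day 673 | none |
| Completer, End of Study Visit and no EDV, tapers | Day 701 | none |
| Same completer under protocol 5.1.1 | Day 673 | Day 674–701 |

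**4. Share of the Evaluation Period misassigned.** Taper days / (visit day + taper days):

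- Week 96: 7/680 = 1.0% to 28/701 = 4.0%.
- Month 96 (Day 2880, the last time point in SAP 5.4): 7/2887 = 0.2% to 28/2908 = 1.0%.
- Week 48 (Day 337), only if approval or closure fell then, since it is not a planned completion point: 7/344 = 2.0% to 28/365 = 7.7%.

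**5. Effect on percent reduction (illustration).** Assume a true 50% reduction on treatment, a complete diary and a 28-day taper from Week 96. With frequency as a fraction of Baseline:

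- No change in taper: 1 − 701 × 0.5/701 = 50.0%.
- Last taper week at Baseline: 1 − (694 × 0.5 + 7)/701 = 1 − 354/701 = 49.5%.
- Whole taper at Baseline: 1 − (673 × 0.5 + 28)/701 = 1 − 364.5/701 = 48.0%.
- Whole taper at Baseline, from Month 96: 1 − (1440 + 28)/2908 = 49.5%.

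**6. Three-month efficacy intervals.** SAP 3.2.6 includes a subject if the last Evaluation Period dose reaches the interval's last day. At Week 96 ± 7 days the visit falls on Day 666–680 and the taper ends on Day 673–708. Both lie between the interval ends Day 630 and Day 720, so none is gained. At other exit times one can be: Day 337 + 28 = Day 365 passes Day 360 and adds Months 10–12.

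**The case against.** The best defence is that the two labels mean one visit. Protocol 8.7 and both assessment schedules list the End of Study Visit and the EDV together, with one set of procedures. SAP 3.2.5 also says that the investigator first plans an EDV when a subject is stopping BRV, and a tapering completer is stopping BRV. It separates completers from dropouts by the Study Termination form. If one date serves both labels, the completer rule works.

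That reading needs both labels to carry a date for the same subject. If only an End of Study Visit is recorded, Down-Titration cannot be entered. If only an EDV is recorded, the completer rule has no End of Study Visit date to use. SAP 3.2.5 and footnote i assign the labels to different groups, although footnote i concerns where end-of-study status is recorded, not analysis periods.

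Other points do stand. The intent is visible, so a careful programmer might work around the gap. The misassignment is conditional on no EDV being recorded. The affected group may be small, because converters are exempt and the study can run to approval. The numerical drift is small and all analyses are descriptive. The absence of interval effects holds for Week 96 only, so that part of the effect is understated for other exit times.

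**Conclusion.** The concern holds as a fault in the written algorithm. SAP 3.2.5 contains a rule for tapering completers that its own entry condition blocks when no EDV is recorded, and the resulting default conflicts with protocol 5.1.1. Each affected subject has 7 to 28 planned taper days in the wrong period, or 1.0% to 4.0% of the Evaluation Period at Week 96. Smaller weekly steps are still capped at 4 weeks, and an unfinished taper could be shorter.

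The effect on percent reduction is minor: 50.0% falls to between 49.5% and 48.0% in the two Week 96 scenarios where seizures return to Baseline, and does not move if frequency is unchanged in taper. The more important effects are that withdrawal-phase adverse events are reported under Evaluation, and that a single taper seizure cancels seizure freedom. This rests on the literal text. How the CRF labels the closing visit, and how many completers taper, cannot be seen in the documents. The period rule should not depend on either.

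**What to change.** In SAP 3.2.5:

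- Define entry to Down-Titration as an End of Study Visit (completed subjects) or an EDV (discontinued subjects), plus at least one study-drug dose after the date of that visit.
- Start Down-Titration on the day after that visit and end the Evaluation Period on the visit date.
- Amend the two clauses on subjects without an EDV, and with an EDV but no later dosing, to match.
- State in 3.2.5 itself that converters to commercial BRV are excluded. Otherwise a converter with any study-drug dose dated after the End of Study Visit would be flagged as tapering.

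The cost is one or two SAP sentences and one period-flag derivation. No data collection or protocol change is needed, and the taper schedule is not touched.
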